### **C. Materials, Methods and Analysis**

The proposed study is a two-group randomized controlled trial with separate assessments of patients and spouse care partners at 0, two months and five months. A community-based sample of patient-spouse care partner dyads will be recruited and randomly assigned by block (patient gender) to either the *Taking Care of Us* intervention or to an educational attention-control. All sessions will be delivered via Zoom (or phone) - there will be no in-person contact with participants throughout the study. *The term spouse refers to spouse or*

*unmarried partner.* All participants will be assessed three times baseline, two months and five months. We believe 7 biweekly sessions over two months, with the first follow-up interview taking place immediately at two months is realistic and appropriate. Our second follow-up will take place at five months to explore sustained effects. The attention-control group will receive three educational sessions over two months (at approximately 0-, 4- and 8 weeks). The sampling frame for the proposed research is community-dwelling adults with NYHA class II-III HF and their spouse/partner. The target sample is 72 couples with HF (36 couples per arm) with equal gender representation.

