Eligible and consented dyads will be randomly assigned to one of two groups. Block randomization stratifying by patient gender will be done using an online research randomizer ([www.randomizer.org](http://www.randomizer.org)). We will stratify by patient gender to ensure equal distribution between the two conditions. Participants will be provided with separate e-mail-specific links to the patient and spouse web-based survey using our REDCap platform; baseline surveys will take approximately 45 minutes to complete. Participants will be instructed to complete the survey separately without discussing the questions with their spouse/anyone else (this procedure has been successfully used in all dyadic work by this team and is the standard procedure in couple research). Participants who do not want to or cannot complete the survey electronically will be offered the option to complete the survey with a trained interviewer (blinded with respect to treatment assignment) via Zoom, phone or to complete a mail survey. Patients and their spouses will be interviewed separately and privately as in our other dyadic research. For the few participants who request a mail survey, they will receive individual packets and consent forms and return the survey and signed consent form in the stamped, addressed envelope provided. These procedures are identical to those successfully used by this team in other couple studies.

All Taking Care of US© (TCU) and educational sessions will be conducted via Zoom (or phone). Relevant materials for the sessions will be mailed to dyads ahead of the first session. For dyads in the TCU group, the project coordinator will inform the interventionist to schedule the first session with the dyad. The interventionist will communicate the treatment assignment to the dyad. Following completion of the 7 sessions of TCU, the interventionist will inform the project coordinator, who will schedule the immediate post-treatment interviews. For the control group, the trained educator (not involved in data collection) will contact the dyad to communicate their assignment to the attention-control condition and schedule a time for their first education session. Two additional education sessions will be done at 4 and 8 weeks. Following completion of the final education session, the trained educator will inform the project coordinator, who will schedule the immediate post-treatment interviews (approximately two months).

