*individual health (i.e., lower care-related strain and better HF-specific QOL) compared with HF dyads in the control group.* Aim 2: To determine the efficacy of the *Taking Care of Us* intervention on dyadic appraisal & dyadic management. *Hypothesis: HF dyads in the Taking Care of Us group will have more similar appraisal of patient symptoms (i.e., dyspnea, pain, fatigue), greater collaboration in HF management behaviors and shared activities, and greater communication and dyadic confidence compared with HF dyads in the control group.* For Aims 1 & 2 we will have the following procedures. First, we will run a series of longitudinal APIM (matched pairs) models to simultaneously examine patient and care partner trajectories in health, depressive symptoms, anxiety, perceived dyadic health and healthcare utilization (Aim 1), engagement in heart failure behaviors, shared activities, communication and confidence (Aim 2) over time (controlling for interdependent data). Each HLM Level 1 model has four coefficients representing intercepts (baseline assessments) and slopes (rates of change) for patients and care partners that become outcome variables in an unconditional Level 2 model. Conditional Level 2 models will examine the effect of GROUP on patient and care partner dyadic health and dyadic management variables (controlling for covariates). A significant coefficient for GROUP on the slope parameter and a significantly better fitting model (as evidenced by the deviance statistic) will indicate the rate of change across time is statistically dependent on treatment condition. Second, to examine dyadic symptom appraisal, a longitudinal incongruence model will be used to directly examine patient-care partner dyadic appraisal over time where the slope represents the pattern of change in incongruence (gap in appraisal between the two members of the dyad). Three separate models will be estimated for each outcome (patient dyspnea, pain, & fatigue). We will know how large the gap is, the type of gap (e.g., care partner rating lower than patient), how the gap changes over time (e.g., increases, decreases, remains stable), and how much variability there is around the average pattern of change. The effect of TCU on dyadic appraisal will be tested directly by examining the role of GROUP. Third, for individual level variables (i.e., care strain and HF-QOL) individual MLM will be used to examine the role of GROUP.

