### **Research Population & Recruitment Methods:**

The sampling frame for the proposed research is community-dwelling adult women and men with HF and their spouse care partner.

Formal inclusion and exclusion criteria for patient participants are:

Inclusion criteria:

Willing and able to provide written informed consent

Age greater than or equal to 18 years

Diagnosis of HF

Current HF symptoms (i.e. NYHA Class II-III; AHA/ACC Stage C HF)

Reachable by telephone/email/texting

Access to device with camera (e.g., computer, tablet) to participate in Zoom sessions or phone

Have a co-residing spouse/unmarried partner willing to participate

Exclusion criteria:

Major and uncorrected hearing impairment

Significant cognitive impairment

Heart transplantation/mechanical circulatory support prior to enrollment

Concomitant terminal illness that would impede participation in a longitudinal study

Active psychosis or severe substance abuse that would impair the ability to complete the study

Inability to complete the requirements of the study, including enrolment in an additional intervention trial

Formal inclusion criteria for spouse care partner participants are:

Age greater than or equal to 18 years

Co-residing with the patient at the time of recruitment

Have lived with the patient for a minimum of one year similar to other couple studies

Be willing and able to provide written informed consent

*Inclusion Criteria Justification:* An approximately equal number of women and men with heart failure will be enrolled. No potential participant will be excluded based on gender, race or ethnicity.

With 72 couples (144 participants total), and allowing for a 17% missing data rate, i.e. 60 dyads), we have 80% power to detect a 6.6 point difference in dyadic PROMIS global health scores between intervention and control groups (score mean=50, SD=10), which is greater than a minimally clinically important difference (estimate of  $\frac{1}{2}$  SD (5) due to no additional estimates available). These preliminary data are required to determine the sample size needed for a larger trial.

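### The plan does not say whether GROUP enters the baseline-intercept equations, and nothing in it uses the common baseline mean that randomisation provides or adjusts for the baseline score; on the likely reading the slope test is valid but less precise than it could be

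*Combined protocol and SAP*

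**What the plan says.** The analysis text for Aims 1 and 2 stands at the end of section C, after the measures for Aim 3. It sets up the growth model as follows: "Each HLM Level 1 model has four coefficients representing intercepts (baseline assessments) and slopes (rates of change) for patients and care partners". The same sentence makes these coefficients the outcomes of an unconditional Level 2 model, that is, one without GROUP. The next step is: "Conditional Level 2 models will examine the effect of GROUP on patient and care partner dyadic health and dyadic management variables". No equations are named. The treatment effect is read from the GROUP coefficient on the slope together with a deviance comparison. For the incongruence models (dyspnea, pain, fatigue) and the individual models (care strain, HF-specific QOL), the text says only that the role of GROUP will be examined.

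Covariates are to be chosen by their correlation with each outcome; the baseline score is not named. On allocation, section C states: "Eligible and consented dyads will be randomly assigned to one of two groups", in blocks stratified by patient gender.

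**The concern.** Because dyads are randomised, the expected baseline difference between arms is zero. A model that gives GROUP its own effect on each intercept estimates that known zero and pays for it in the variance of the slope contrast. A chance imbalance at baseline then also feeds into the slope contrast through regression to the mean. With about 60 analysable dyads expected, precision is scarce, and recovering it needs no new data. The same question arises for the primary outcome and for every other Aim 1 and Aim 2 growth model. It is separate from the straight-line form of time, the covariate rule and the deviance rule.

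**Working it through.** **The plan's own figure.** Under Research Population & Recruitment Methods the plan says "we have 80% power to detect a 6.6 point difference in dyadic PROMIS global health scores between intervention and control groups", with "score mean=50, SD=10" and "allowing for a 17% missing data rate, i.e. 60 dyads". Alpha and sidedness are not stated. Normal approximation, 5% level:

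- 30 dyads per arm: SE = 10 × √(2/30) = 2.582 and 6.6/2.582 = 2.556. One-sided: 2.556 − 1.645 = 0.911, power 81.9%. Two-sided: 2.556 − 1.960 = 0.596, power 72.4%.
- 36 per arm (all 72 dyads): SE = 2.357 and 6.6/2.357 = 2.800. Two-sided power 80.0%.

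So the 80% is reproduced at 60 dyads only with a one-sided test, or with a two-sided test at 72. That is a separate matter. What counts here is that the calculation is a plain two-group difference with no credit for baseline.

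**Inputs for the precision check.** From section C: waves at t = (0, 2, 5) months and equal arms. Assumed, because the documents give no value: between-wave correlation ρ, compound symmetry, no random-slope variance, complete data.

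**Formulas.** Σt = 7 and Σt² = 29. With V the within-person correlation matrix, the information on the GROUP slope, up to a common factor, is:

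- GROUP on intercept and slope: t′V⁻¹t − (t′V⁻¹1)²/(1′V⁻¹1) = (29 − 49/3)/(1 − ρ) = 12.667/(1 − ρ).
- GROUP on slope only: t′V⁻¹t = [29 − 49ρ/(1 + 2ρ)]/(1 − ρ).

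The variance ratio, first model over second, is [29 − 49ρ/(1 + 2ρ)]/12.667.

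| ρ | numerator | ratio | dyads needed to match 60 |
|---|---|---|---|
| 0.3 | 29 − 9.188 = 19.813 | 1.564 | 93.8 |
| 0.5 | 29 − 12.250 = 16.750 | 1.322 | 79.3 |
| 0.6 | 29 − 13.364 = 15.636 | 1.234 | 74.1 |
| 0.7 | 29 − 14.292 = 14.708 | 1.161 | 69.7 |
| 0.8 | 29 − 15.077 = 13.923 | 1.099 | 66.0 |
| 0.9 | 29 − 15.750 = 13.250 | 1.046 | 62.8 |

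**Why it acts like a change score.** In the first model the three waves are weighted (t − 7/3)/12.667 = (−0.184, −0.026, +0.211). These sum to zero, so baseline is subtracted in full whatever ρ is. In the second model the weights are [t − 7ρ/(1 + 2ρ)] divided by the numerator above. At ρ = 0.6 they are (−0.122, +0.006, +0.198): baseline counts for less, as in a baseline-adjusted analysis.

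**In power terms (two-sided 5%).** If the slope-only model had 80% power (standardised effect 2.802), the other would have 2.802/√1.161 − 1.960 = 0.640, or 74%, at ρ = 0.7. At ρ = 0.5 it would have 2.802/√1.322 − 1.960 = 0.477, or 68%.

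**Sensitivity.**

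- 17% of dyads lost after baseline: ratio 1.273 at ρ = 0.5 and 1.135 at ρ = 0.7.
- Random slopes (assumed baseline intraclass correlation 0.5 to 0.7, slope SD 0.5 to 1.5 points per month, intercept-slope correlation −0.5 to +0.3): ratio 1.007 to 1.628.
- Patient and partner modelled jointly: ratio unchanged when the within-dyad correlation is the same for intercepts and residuals; otherwise 1.11 to 1.36 for ρ 0.5 to 0.7.

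**Against the power statement.** In the first model the variance of the 5-month contrast, relative to a single-time comparison, is 25(1 − ρ)/12.667 = 1.974(1 − ρ). That is 0.99 at ρ = 0.5 and 0.59 at ρ = 0.7, so under these assumptions and a linear effect it does no worse than the design calculation assumed.

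**The case against.** The strongest reply is that the plan never puts GROUP on the intercepts. The sentence listing intercepts and slopes describes the model before GROUP enters, and the only GROUP coefficient named is the one on the slope. The text is therefore compatible with the model recommended here. This stands: a reader might infer that the plan assigns GROUP an effect at baseline, but the documents only leave that open. They equally contain no common baseline mean and no baseline covariate, so the sentence is needed on either reading.

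Three other inferences go too far.

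- The 16% to 32% is not a property of this trial. It belongs to assumed correlations of 0.7 to 0.5 under compound symmetry with complete data and no slope variance, whereas the plan expects missing data and treats slopes as Level 2 outcomes.
- Baseline data are not thrown away. Baseline is the first wave in the model, and only the knowledge that the arms share a baseline mean would go unused.
- The trial is not underpowered against its own statement for this reason, because that statement takes no credit for baseline.

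The remedy also has a precondition. Section C describes assignment first and the survey links afterwards. It says who tells the dyad its arm, but not that baseline surveys must be complete by then. If some dyads answered knowing their arm, forcing equal baseline means could introduce bias.

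**Conclusion.** The point holds as a gap in specification with a likely cost in efficiency. If GROUP is placed on all four equations, the treatment test remains valid over randomisation, with no bias or inflation of type I error from this source, but it is less precise than it need be. With a correctly specified covariance, the common-baseline constraint cannot increase the variance of the slope contrast; only the size of the gain is uncertain. The illustrative loss equals 16% to 32% more dyads for assumed correlations of 0.7 to 0.5, 5% to 56% across 0.9 to 0.3, and roughly 1% to 63% with random slopes. The documents supply none of these inputs, so the figures should be read as a range and not as an estimate for this trial. The change is worth making because it costs almost nothing in a small pilot whose results will size a larger study.

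**What to change.** State in the analysis text for Aims 1 and 2 which Level 2 equations contain GROUP. Keep GROUP on the slopes and omit it from the baseline-intercept equations, so that both arms share one baseline mean per role (and one baseline gap in the incongruence models). Alternatively, model the follow-up scores with each member's own baseline score as a covariate. Use the same rule in the individual models, and show baseline means by arm descriptively.

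Add a sentence to section C confirming that both members complete the baseline survey before the arm is communicated. If that cannot be assured for every dyad, say how the exceptions will be handled.

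The cost is a sentence of analysis wording and a sentence on timing. The planned HLM software can fit the model by leaving GROUP out of two equations, and no new data are needed.

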#### Measures Relevant to Aim 1 (Dyadic & Individual Health)

General health: The 10-item PROMIS Global Health short form will be used as a general measure of QOL for patients and care partners. The measure includes specific ratings of physical, mental and overall QOL.

Depressive symptoms: The Center for Epidemiological Studies-Depression (CES-D) scale is a widely used measure of depressive symptoms. Participants respond to 20 statements (based on feelings during the past week) using the response categories 1=rarely or none, 2=some or a little, 3=occasionally or moderate, and 4=most or all. The potential range of scores is 0-60, with higher scores indicating greater depressive symptomatology. The CES-D scale has been widely used with older adults, demonstrating good internal consistency with Cronbach's alpha in the .86 to .92 range in samples of FMs and cancer PTs. Sensitivity, specificity and validity of the scale have also been supported. Anxiety: Patient and care partner anxiety will be measured using the 4-item PROMIS Anxiety short form.

Healthcare Utilization: The Stanford Patient Education Research Center (PERC) Healthcare Utilization assessment will be used at 0 and 28 weeks to collect physician, mental health, emergency room visits and hospitalizations for both patients and care partners. Care-related strain: The Multidimensional Caregiver Strain Index (MCSI) will be used to capture physical, social and interpersonal strain, time constraints and demands.

HF-Specific QOL: The Kansas City Cardiomyopathy Questionnaire (KCCQ), a 12-item Likert scale will be used to measure patient HF-specific quality-of-life. Scores range from 0-100 with higher scores reflecting better QOL. Cronbach's alpha on these subscales range from 0.75-0.85.

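### Healthcare utilization, scheduled at two times only, is assigned a four-coefficient growth model whose variance components two times cannot identify, and no two-wave analysis is stated

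*Combined protocol and SAP*

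**What the plan says.** Under Measures Relevant to Aim 1, the "Healthcare Utilization assessment will be used at 0 and 28 weeks to collect physician, mental health, emergency room visits and hospitalizations" for patients and care partners. No recall period is given.

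The analysis text for Aims 1 and 2 (section C, after Measures Relevant to Aim 3) fits longitudinal matched-pairs models to "trajectories in health, depressive symptoms, anxiety, perceived dyadic health and healthcare utilization (Aim 1"). In these models, "Each HLM Level 1 model has four coefficients representing intercepts (baseline assessments) and slopes (rates of change) for patients and care partners". All four of these are then carried up as Level 2 outcomes. Treatment is judged by "A significant coefficient for GROUP on the slope parameter and a significantly better fitting model (as evidenced by the deviance statistic"). Care strain and HF-specific quality of life get a separate individual-level model. Utilization gets no exception, two-wave variant, distribution or link.

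The design paragraph of section C says "All participants will be assessed three times baseline, two months and five months". No wave falls at 28 weeks. The general list of survey content includes utilization without saying at which waves.

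**The concern.** A growth model with a random intercept and a random slope for each member needs more than two occasions to separate true change from residual noise. Utilization has two. An analyst who follows the text would have to simplify the model, and the plan does not say how. The choice would then be made after the data are in.

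Even when simplified, a two-wave slope is only a change score. With noisy visit counts, unadjusted change is usually an inefficient basis for a treatment comparison. Less utilization is a named part of the Aim 1 hypothesis, and the sample-size paragraph says the pilot's data are needed to size a larger trial.

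**Working it through.** **Inputs from the documents.** Two occasions (0 and 28 weeks); two members per dyad; four Level 1 coefficients; "The target sample is 72 couples with HF (36 couples per arm"), reduced to 60 dyads (30 per arm) after the 17% allowance for missing data. The only power figure in the documents concerns PROMIS global health, so there is no plan figure for utilization to reproduce.

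**1. Count of moments and parameters.** Reading all four coefficients as random:

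- Observed moments with two times: 2 × 2 = 4 values per dyad, so 4 × 5 / 2 = 10 variances and covariances.
- Parameters: 4 × 5 / 2 = 10 for the random coefficients, plus 1 residual variance = 11 (12 with a residual variance per role).
- Rank of the map from parameters to moments: 10 with two times, so not identified.
- With three times: 6 × 7 / 2 = 21 moments, and the rank equals the number of parameters (11 of 11), so identified.

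**2. Why it fails.** For one member at times 0 and T, with intercept variance a, intercept-slope covariance b, slope variance d and residual variance s:

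- Var(y0) = a + s
- Cov(y0, yT) = a + Tb
- Var(yT) = a + 2Tb + T²d + s

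Replace s by s + c, a by a − c, b by b + c/T and d by d − 2c/T². All three expressions are unchanged; in the last, −c + 2c − 2c + c = 0. Slope variance and residual variance therefore trade off freely.

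**3. Fixed effects.** With GROUP on all four coefficients there are 8 fixed effects and the design has rank 8, so they are identified. The GROUP-on-slope coefficient is the between-group difference in mean change divided by the elapsed time.

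**4. Why the restriction matters.** Fixing the residual variance leaves the 10 moments free. Dropping the random slopes instead forces equal variance at both times within a role and, with a common residual, equal change variance for patients and care partners. Standard errors can then differ between the two choices, and so can the deviance.

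**5. Power of the two-wave slope test.** Suppose GROUP is also on the intercept. With equal variances and a baseline-to-follow-up correlation r, the variance is 2σ²(1 − r) for change and σ²(1 − r²) for follow-up adjusted for baseline. The ratio of adjusted to change is (1 + r)/2. The simulations below had r from 0.04 to 0.48 under no effect, so the ratio runs from 0.52 to 0.74.

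The simulations used overdispersed counts for one member, rate ratio 0.5, 30 per arm, two-sided 0.05 and 1,200 trials per row. All rates and dispersions are assumptions.

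| Mean visits | Frailty variance | Stable share | Change | Adjusted linear | Adjusted count | Linear − change | Count − linear |
|---|---|---|---|---|---|---|---|
| 0.3 | 0.5 | 0.3 | 11.2% | 19.9% | 16.2% | 8.7 | −3.7 |
| 0.3 | 1.0 | 0.8 | 10.7% | 17.2% | 13.8% | 6.5 | −3.4 |
| 1 | 0.5 | 0.3 | 24.8% | 48.0% | 50.1% | 23.2 | 2.1 |
| 1 | 1.0 | 0.8 | 24.2% | 39.0% | 42.2% | 14.8 | 3.2 |
| 3 | 0.5 | 0.3 | 43.4% | 74.1% | 76.7% | 30.7 | 2.6 |

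The count model is quasi-Poisson, adjusted for log(baseline + 0.5). Type I error was about 4–6% for all three methods.

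Runs with frailty variance 1–2 gave, in the same order (change / adjusted linear / adjusted count):

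- Mean 1: 28–30% / 37–43% / 40–44%.
- Mean 3: 59–65% / 77–86% / 81–88%.
- Mean 0.3: adjusted linear 15%, adjusted count 11–12%.

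The loss in these runs at means 1 and 3 is roughly 7 points (37 − 30) to 22 points (81 − 59).

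**6. Timing.** Five months is 5 × 52 / 12 ≈ 22 weeks, about 6 weeks short of 28.

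**The case against.** A reader might infer that the treatment effect on utilization cannot be estimated at all. The documents do not support that. The failure lies in the variance components. GROUP on slope can be estimated once the random part is restricted, and the text does not say outright that all four coefficients carry a random residual. What stands is that the plan states no restriction.

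A reader might also infer that a linear model is wrong for counts and wastes power for that reason. The simulations do not show this. The linear tests held their error rate, and a baseline-adjusted linear model recovers nearly all of the loss. The count link adds about 0 to 5 points at means 1 to 3 and does worse than adjusted linear at mean 0.3, the rare-event case.

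The power loss also depends on GROUP being on the intercept. The decision rule names only the slope. If the baseline mean is common to both arms, the model in effect adjusts for baseline, and much of the gap should close. This objection stands as a condition on the size.

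The plan does say that multilevel models tolerate different numbers and spacing of waves. That is said of differences between dyads. It does not help an outcome for which every dyad has at most two.

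Finally, utilization may in fact be collected at every survey, since the list of survey content sets no limit. The identification problem would then disappear. That is a reason to settle the schedule first.

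**Conclusion.** The point holds in a limited form. As scheduled, utilization yields 10 covariance moments for the 11 parameters of the stated model with all four coefficients random, so that model cannot be fitted to this outcome without a constraint that the plan does not give. This result needs no assumption about visit rates.

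The power loss is conditional and illustrative. If GROUP is on the intercept, testing unadjusted change costs roughly 7 to 22 points at mean 1 to 3 visits, rate ratio 0.5 and frailty variance 1–2. It costs about 15 to 31 points in the less dispersed settings. The cause is the missing baseline adjustment rather than the linear scale. The documents give no visit rate, dispersion or target effect, so no loss can be measured for this trial.

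The 28-week time matches no study wave, which is a contradiction in its own right. Utilization is not the primary outcome, and the three-wave model for the primary outcome is identified. The change should be made, but the trial's main conclusion does not depend on it.

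**What to change.** 1. Reconcile the 28-week time point with the 0, two- and five-month surveys, and state one recall window that applies in both arms.
2. If utilization is collected at two times, take it out of the growth-model list. Analyse the follow-up value adjusted for its baseline value, with GROUP, patient gender and member role, and clustering by dyad. A log-link count model with dispersion-corrected errors gives a readable rate ratio with a 95% interval. For very rare events, specify a baseline-adjusted linear model or a combined visit count instead. State in advance whether the visit types are analysed separately or together.
3. If it is collected at all three waves, the growth model is identified and can stay. The plan should then say so, state whether GROUP enters the intercept, and still give the recall window and the treatment of counts.

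The cost is analysis-plan wording and, with two times, one extra model type for an outcome that is not primary. No new data are needed.
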